9.4.4 Pharmacokinetic endpoints

Trough (pre-dose) concentrations (C_{trough}) for 3 dose levels of BAY 2976217 will be summarized descriptively by dose level and visit (i.e. V12, V14, V16, V18). Details will be specified in SAP.

9.4.5 Pharmacodynamic endpoints

The PD profile will be assessed as described in Section 8.6.

• Changes in FXI antigen levels and FXI activity levels:

Maximum change in FXI activity and antigen levels during the main treatment period will be summarized by treatment groups.

9.4.6 Tertiary/exploratory endpoints

Further details on exploratory endpoints (e.g. biomarker and immunogenicity analyses) are described in the SAP.

9.4.6.1 Exploratory efficacy endpoints

The exploratory efficacy endpoints, as assessed by the CIAC, are:

- Incidence of composite and event types of death due to MI, stroke, PE and SE, and non-fatal stroke, non-fatal MI, VTE, major amputation of vascular etiology, and acute limb ischemia
- Incidence of thrombosis of the arterio-venous grafts or fistulas.

9.4.6.2 Other pre-specified safety endpoints

All safety analyses will be made on the Safety Population.

• Incidence and severity of AESIs:

Hepatic enzyme elevation, thrombocytopenia

• Changes in blood pressure, laboratory assessments:

Laboratory tests (see Section 8.2.4) to ensure subject safety including chemistry/liver panel, coagulation panel, hematology panel etc., will be summarized by study visits for each treatment group. These safety variables will also be presented as change and percent change from Baseline over time after study intervention (BAY 2976217 or placebo) administration, as appropriate. In addition, the number of subjects who experience abnormalities in clinical laboratory evaluations will be summarized by treatment group.

• Incidence and severity of bleeding of the arterio-venous grafts or fistulas:

All events of arterio-venous graft or fistula bleeding, in excess of expected postdialysis bleeding or requiring additional hemostatic measures than usual, will be reported as an AE or SAE as per adverse event reporting procedure in Section 8.3. The incidence and severity of the events will be summarized by treatment group.

Additionally, assessment of the severity of bleeding at the dialysis access following the hemodialysis procedure will be done at specified visits. Severity of bleeding at the dialysis access will be assessed approximately 15 minutes after removal of the dialysis needle(s) from the AV access according to the following categories (exploratory bleeding score):

07 JUL 2021 Page: 68 of 90

- "0" no access bleeding
- "1" slow oozing
- "2" overt bleeding

The proportion of the participants with the bleeding at the dialysis access following the hemodialysis procedure will be summarized by treatment group according to the above 3 bleeding score categories.

9.4.6.3 Pre-specified PD endpoints

• Changes in PT, INR, and aPTT:

Maximum change in PT, INR, and aPTT levels during the main treatment period will be summarized by treatment group.

• Extent and frequency of clotting on the dialysis filters & circuit:

The extent and occurrence of clotting on the dialysis filters and circuit will be summarized descriptively by category scoring (SQCS) as described in Section 8.6. For a change from baseline to evaluation period analysis, the baseline for liver enzymes, platelets, PD biomarkers including the clotting score, AV access bleeding score will be the mean of measurements taken during the 1-week screening period. The final 4 weeks (Visits 19-22) would be the evaluation period from which a mean value can be determined from measurements taken during this period.

• Changes in d-dimers:

Change and percent change in d-dimers will be tabulated by treatment group by study visit.

- TAT
- F1.2

9.4.7 Other analyses

Analysis of COVID-19 Patients

Analysis to evaluate the COVID-19 impact on the study primary safety and exploratory efficacy endpoints will be performed by comparing the descriptive statistics among confirmed COVID-19 versus non-COVID-19 patient population. Additional COVID-19 analysis considerations will be described in the SAP.

9.5 Interim Analyses

No formal interim analysis is planned.

9.6 Data Monitoring Committee (DMC)

An independent data monitoring committee will monitor the safety of the participants. For details on DMC, see Section 10.1.5.

07 JUL 2021 Page: 69 of 90

10. Supporting Documentation and Operational Considerations

10.1 Appendix 1: Regulatory, Ethical, and Study Oversight Considerations

10.1.1 Regulatory and Ethical Considerations

- This study will be conducted in accordance with the protocol and with the following:
- Consensus ethical principles derived from international guidelines including the Declaration of Helsinki and Council for International Organizations of Medical Sciences International Ethical Guidelines
 - Applicable ICH GCP Guidelines
 - Applicable laws and regulations
- The protocol, protocol amendments, ICF, Investigator Brochure, and other relevant documents (e.g., advertisements) must be submitted to an IRB/IEC by the investigator and reviewed and approved by the IRB/IEC before the study is initiated.
- Any amendments to the protocol will require IRB/IEC approval before implementation of changes made to the study design, except for changes necessary to eliminate an immediate hazard to study participants. Any substantial modification of the protocol will be submitted to the competent authorities as substantial amendments for approval, in accordance with ICH Good Clinical Practice and national and international regulations.
- The investigator will be responsible for the following:
- Providing written summaries of the status of the study to the IRB/IEC annually or more frequently in accordance with the requirements, policies, and procedures established by the IRB/IEC
- Notifying the IRB/IEC of SAEs or other significant safety findings as required by IRB/IEC procedures
- Providing oversight of the conduct of the study at the site and adherence to requirements, ICH guidelines, the IRB/IEC, and all other applicable local regulations

10.1.2 Financial Disclosure

Investigators and sub-investigators will provide the sponsor with sufficient, accurate financial information as requested to allow the sponsor to submit complete and accurate financial certification or disclosure statements to the appropriate regulatory authorities. Investigators are responsible for providing information on financial interests during the course of the study and for 1 year after completion of the study.

10.1.3 Informed Consent Process

• The investigator or his/her representative will explain the nature of the study to the participant or his/her legally authorized representative and answer all questions regarding the study.

07 JUL 2021 Page: 70 of 90

- Participants must be informed that their participation is voluntary. Participants or their legally authorized representative will be required to sign a statement of informed consent that meets the requirements of 21 CFR 50, local regulations, ICH guidelines, Health Insurance Portability and Accountability Act requirements, where applicable, and the IRB/IEC or study center.
- The medical record must include a statement that written informed consent was obtained before the participant was enrolled in the study and the date the written consent was obtained. The authorized person obtaining the informed consent must also sign the ICF.
- Participants must be re-consented to the most current version of the ICF(s) during their participation in the study.
- A copy of the ICF(s) must be provided to the participant or the participant's legally authorized representative.
- Participants who are rescreened are required to sign a new ICF.
- The following ICFs are available for the study:
 - o Regular ICF for study entry;
 - o Regular ICF for study entry for alternative PK&PD sampling group;
 - o Pregnancy ICF for female participants for follow-up data;
 - o Pregnancy ICF for male participants for follow-up data.

10.1.4 Data Protection

- Participants will be assigned a unique identifier by the sponsor. Any participant records or datasets that are transferred to the sponsor will contain the identifier only; participant names or any information which would make the participant identifiable will not be transferred.
- The participant must be informed that his/her personal study-related data will be used by the sponsor in accordance with local data protection law. The level of disclosure must also be explained to the participant who will be required to give consent for their data to be used as described in the informed consent.
- The participant must be informed that his/her medical records may be examined by Clinical Quality Assurance auditors or other authorized personnel appointed by the sponsor, by appropriate IRB/IEC members, and by inspectors from regulatory authorities.

10.1.5 Committees Structure

The primary role of the DMC is to periodically review the safety data and ensure the safety of the participants in the ongoing study including unblinded data. The full description of the DMC structure and tasks is provided in the DMC charter.

A Study Steering Committee will be established to provide medical consultancy. The full description of the Steering Committee structure and tasks is provided in the Steering Committee charter.

CIAC is blinded for treatment allocation and will objectively assess the incidence of major bleeding and clinically relevant non-major bleeding as well as all suspected bleeding and thrombosis events. The full description of the CIAC structure and tasks is provided in the CIAC charter.

07 JUL 2021 Page: 71 of 90

10.1.6 Dissemination of Clinical Study Data

Result Summaries of Bayer's sponsored clinical trials in drug development Phases 2, 3 and 4 and Phase 1 studies in patients are provided in the Bayer Trial Finder application after marketing authorization approval in line with the position of the global pharmaceutical industry associations laid down in the "Joint Position on the Disclosure of Clinical Trial Information via Clinical Trial Registries and Databases. In addition, results of clinical drug trials will be provided on the publicly funded website www.ClinicalTrials.gov and EU Clinical Trials Register in line with the applicable regulations.

Bayer commits to sharing upon request from qualified scientific and medical researchers participant-level clinical trial data, study-level clinical trial data, and protocols from clinical trials in patients for medicines and indications approved in the United States (US) and European Union (EU) on or after 01 JAN 2014 as necessary for conducting legitimate research.

All Bayer-sponsored clinical trials are considered for publication in the scientific literature irrespective of whether the results of the clinical trials are positive or negative.

10.1.7 Data Quality Assurance

- All participant data relating to the study will be recorded on printed or electronic CRF unless transmitted to the sponsor or designee electronically (e.g., laboratory data). The investigator is responsible for verifying that data entries are accurate and correct by physically or electronically signing the CRF.
- The investigator must maintain accurate documentation (source data) that supports the information entered in the CRF.
- The investigator must permit study-related monitoring, audits, IRB/IEC review, and regulatory agency inspections and provide direct access to source data documents.
- Monitoring details describing strategy (e.g., risk-based initiatives in operations and quality such as Risk Management and Mitigation Strategies and Analytical Risk-Based Monitoring), methods, responsibilities and requirements, including handling of noncompliance issues and monitoring techniques (central, remote, or on-site monitoring) are provided in the Monitoring Plan.
- The sponsor or designee is responsible for the data management of this study including quality checking of the data.
- The sponsor assumes accountability for actions delegated to other individuals (e.g., Contract Research Organizations).
- Study monitors will perform ongoing source data verification to confirm that data
 entered into the CRF by authorized site personnel are accurate, complete, and
 verifiable from source documents; that the safety and rights of participants are being
 protected; and that the study is being conducted in accordance with the currently
 approved protocol and any other study agreements, ICH GCP, and all applicable
 regulatory requirements.
- Records and documents, including signed ICFs, pertaining to the conduct of this study
 must be retained by the investigator for 15 years after study completion unless local
 regulations or institutional policies require a longer retention period. No records may
 be destroyed during the retention period without the written approval of the sponsor.
 No records may be transferred to another location or party without written notification
 to the sponsor.

07 JUL 2021 Page: 72 of 90

10.1.8 Source Documents

- Source documents provide evidence for the existence of the participant and substantiate the integrity of the data collected. Source documents are filed at the investigator's site.
- Data reported on the eCRF or entered in the eCRF that are transcribed from source documents must be consistent with the source documents or the discrepancies must be explained. The investigator may need to request previous medical records or transfer records, depending on the study. Also, current medical records must be available.
- Definition of what constitutes source data can be found in a source document check list.

10.1.9 Study and Site Start and Closure

First Participant First Visit is considered the first act of recruitment and will be the study start date.

The sponsor designee reserves the right to close the study site or terminate the study at any time for any reason at the sole discretion of the sponsor. Study sites will be closed upon study completion. A study site is considered closed when all required documents and study supplies have been collected and a study-site closure visit has been performed.

The investigator may initiate study-site closure at any time, provided there is reasonable cause and sufficient notice is given in advance of the intended termination.

Reasons for the early closure of a study site by the sponsor or investigator may include but are not limited to:

- Failure of the investigator to comply with the protocol, the requirements of the IRB/IEC or local health authorities, the sponsor's procedures, or GCP guidelines
- Inadequate recruitment of participants by the investigator
- Discontinuation of further study intervention development

If the study is prematurely terminated or suspended, the sponsor shall promptly inform the investigators, the IECs/IRBs, the regulatory authorities, and any contract research organization(s) used in the study of the reason for termination or suspension, as specified by the applicable regulatory requirements. The investigator shall promptly inform the subject and should assure appropriate subject therapy and/or follow-up.

10.1.10 Publication Policy

- The results of this study may be published or presented at scientific meetings. If this is foreseen, the investigator agrees to submit all manuscripts or abstracts to the sponsor before submission. This allows the sponsor to protect proprietary information and to provide comments.
- The sponsor will comply with the requirements for publication of study results. In accordance with standard editorial and ethical practice, the sponsor will generally support publication of multicenter studies only in their entirety and not as individual site data. In this case, a coordinating investigator will be designated by mutual agreement.
- Authorship will be determined by mutual agreement and in line with International Committee of Medical Journal Editors authorship requirements.

07 JUL 2021 Page: 73 of 90

10.2 Appendix 2: Clinical Laboratory Tests

- The tests detailed in Table 10–1 will be performed by the central laboratory.
- Local laboratory results are required if central laboratory kits are not available, or
 central laboratory results are not available. If a local sample is required, if possible
 a sample for central analysis should be obtained at the same time. Additionally, if
 the local laboratory results are used to make either a study intervention decision or
 response evaluation, the results must be entered into the eCRF. Local laboratory
 results should not be used for eligibility check.
- Protocol-specific requirements for inclusion or exclusion of participants are detailed in Section 5 of the protocol.
- Additional tests may be performed at any time during the study as determined necessary by the investigator or required by local regulations.
- Pregnancy Testing, See Section 5.1 for screening pregnancy criteria.

Table 10-1: Protocol-Required Safety and Routine Laboratory Assessments

Laboratory assessments	Parameters	
Hematology	Hemoglobin, Hematocrit, Red blood cell count (MCV MCH, MCHC, %Reticulocytes), Platelets, white blood cell count with differential (Neutrophils, Lymphocytes, Monocytes, Eosinophils, Basophils)	
Blood Chemistry ¹	Sodium, Potassium, Phosphorus, Magnesium, calcium, chloride, bicarbonate, Creatinine, BUN, Total protein, Albumin Amylase, lipase Creatine kinase, high-sensitivity C-reactive protein, troponin T, NT-pro BNP Lactate dehydrogenase	
Liver enzymes	AST (=ASAT / GOT), ALT (=ALAT/GPT), alkaline phosphatase (ALP), γ-GT, GLDH, TBL, Direct bilirubin, Indirect bilirubin	
Carbohydrate metabolism	HbA1c	
Lipids	Total cholesterol, Triglyceride, HDL-cholesterol, LDL-cholesterol	
Dialysate effluent	BAY 2976217 concentrations, 3'- and 5'- 10-mers, and 3'- and 5'- 5-mers FXI antigen, FXI activity, AXIA, FXI concentration, plasma concentrations of BAY 2976217 (as total full-length oligonucleotide, including fully conjugated, partially conjugated, and unconjugated BAY 2976217), Antibodies to BAY 2976217, TAFI and C1 inhibitor activity, TAT and F1.2, Prothrombin time (Quick), aPTT, Fibrinogen, INR, d-dimer.	
PK / PD / immunogenicity sampling / biomarkers		
Other Screening Tests	 Highly sensitive serum human chorionic gonadotropin (HCG) pregnancy test (as needed for WOCBP) Genetic analysis 	

^{1:} Details of liver chemistry assessment and required actions and follow-up assessments after liver stopping or monitoring event are given in Section 8.3.8.2.

ALAT = alanine aminotransferase; ALP = alkaline phosphatase; ALT = alanine aminotransferase; aPTT = activated partial thromboplastin time; ASAT = Aspartate-aminotransferase; AST = aspartate aminotransferase; AXIA = Activated Factor XIa activity, BUN = Blood urea nitrogen; FXI = Coagulation factor XI, GLDH = Glutamate dehydrogenase; GOT = serum glutamic oxaloacetic transaminase; GPT = Garment package test; γ-GT = glutamyltransferase, HbA1c = Hemoglobin A1c; HDL = high-density lipoprotein; INR= international normalized ratio, LDL = low-density lipoprotein; MCH = mean corpuscular hemoglobin, MCHC = mean corpuscular hemoglobin concentration, MCV = mean corpuscular volume, NT-pro BNP = NT-proB-type Natriuretic Peptide, TAFI = Thrombin-activatable fibrinolysis inhibitor; TAT = Thrombin-antithrombin complex; TBL = total bilirubin, WOCBP = Women of childbearing potential

If the platelet value or liver enzyme tests are uninterpretable (e.g., due to clumping, hemolysis or quantity not sufficient) or missing, a repeat blood specimen should be re-drawn as soon as

07 JUL 2021 Page: 74 of 90

possible (ideally at the next dialysis session) and reviewed prior to dosing. Valid platelet counts and liver enzymes must be obtained at least every 2 weeks and reviewed prior to dosing.

Investigators must document their review of each laboratory safety report.

PD results including coagulation parameters that could unblind the study will not be reported to investigative sites or other blinded personnel until the study has been unblinded.

10.3 Appendix 3: Adverse Events: Definitions and Procedures for Recording, Evaluating, Follow-up, and Reporting

10.3.1 Definition of AE

AE Definition

- An AE is any untoward medical occurrence in a patient or clinical study participant, whether or not considered related to the study intervention.
- NOTE: An AE can therefore be any unfavorable and unintended sign (including an abnormal laboratory finding), symptom, or disease (new or exacerbated) whether or not associated with the use of study intervention.

Events Meeting the AE Definition

- Any abnormal laboratory test results (hematology, clinical chemistry, or urinalysis) or other safety assessments (e.g., ECG, radiological scans, vital signs measurements), including those that worsen from baseline, considered clinically significant in the medical and scientific judgment of the investigator (i.e., not related to progression of underlying disease).
- Exacerbation of a chronic or intermittent pre-existing condition including either an increase in frequency and/or intensity of the condition.
- New conditions detected or diagnosed after study intervention administration even though it may have been present before the start of the study.
- Signs, symptoms, or the clinical sequelae of a suspected drug-drug interaction.
- Signs, symptoms, or the clinical sequelae of a suspected overdose of either study
 intervention or a concomitant medication. Overdose per se will not be reported
 as an AE/SAE unless it is an intentional overdose taken with possible
 suicidal/self-harming intent. Such overdoses should be reported regardless of
 sequelae.
- The signs, symptoms, and/or clinical sequelae resulting from lack of efficacy will be reported as AE or SAE if they fulfil the definition of an AE or SAE. Also, "lack of efficacy" or "failure of expected pharmacological action" also constitutes an AE or SAE.

07 JUL 2021 Page: 75 of 90

Events NOT Meeting the AE Definition

- Any clinically significant abnormal laboratory findings or other abnormal safety assessments which are associated with the underlying disease, unless judged by the investigator to be more severe than expected for the participant's condition.
- The disease/disorder being studied or expected progression, signs, or symptoms of the disease/disorder being studied, unless more severe than expected for the participant's condition.
- Medical or surgical procedure (e.g., endoscopy, appendectomy): the condition that leads to the procedure is the AE.
- Situations in which an untoward medical occurrence did not occur (social and/or convenience admission to a hospital).
- Anticipated day-to-day fluctuations of pre-existing disease(s) or condition(s) present or detected at the start of the study that do not worsen.

10.3.2 Definition of SAE

If an event is not an AE per definition above, then it cannot be an SAE even if serious conditions are met (e.g., hospitalization for signs/symptoms of the disease under study, death due to progression of disease).

An SAE is defined as any untoward medical occurrence that, at any dose:

a. Results in death

b. Is life-threatening

• The term 'life-threatening' in the definition of 'serious' refers to an event in which the participant was at risk of death at the time of the event. It does not refer to an event, which hypothetically might have caused death, if it were more severe.

c. Requires inpatient hospitalization or prolongation of existing hospitalization

- In general, hospitalization signifies that the participant has been detained (usually involving at least an overnight stay) at the hospital or emergency ward for observation and/or treatment that would not have been appropriate in the physician's office or outpatient setting. Complications that occur during hospitalization are AEs. If a complication prolongs hospitalization or fulfills any other serious criteria, the event is serious. When in doubt as to whether "hospitalization" occurred or was necessary, the AE should be considered serious.
- Hospitalization for elective treatment of a pre-existing condition that did not worsen from baseline is not considered an AE.

07 JUL 2021 Page: 76 of 90

d. Results in persistent disability/incapacity

- The term disability means a substantial disruption of a person's ability to conduct normal life functions.
- This definition is not intended to include experiences of relatively minor medical significance such as uncomplicated headache, nausea, vomiting, diarrhea, influenza, and accidental trauma (e.g., sprained ankle) which may interfere with or prevent everyday life functions but do not constitute a substantial disruption.

e. Is a congenital anomaly/birth defect

f. Other situations:

- Medical or scientific judgment should be exercised by the investigator in deciding whether SAE reporting is appropriate in other situations such as significant medical events that may jeopardize the participant or may require medical or surgical intervention to prevent one of the other outcomes listed in the above definition. These events should usually be considered serious.
- Examples of such events include invasive or malignant cancers, intensive treatment for allergic bronchospasm, blood dyscrasias, convulsions, or development of intervention dependency or intervention abuse.

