8.1 Efficacy Assessments

The following efficacy outcomes will be assessed by the blinded CIAC in accordance with the pre-specified endpoint criteria in the adjudication charter:

- Death due to MI, stroke, PE or SE
- Non-fatal MI
- Non-fatal stroke

07 JUL 2021 Page: 42 of 90

- Major amputation of vascular etiology
- Acute limb ischemia (new onset ischemia or worsening or pre-existing ischemia)
- Venous thromboembolism
- Thrombosis of the arterio-venous grafts or fistulas

All deaths and events suspected to be related to cardiovascular disease, or other arterial or venous thrombosis events (including arterio-venous access thrombosis), but not limited to these, will be reported as an AE or SAE as per adverse event reporting procedure in Section 8.3. Additionally, the event will be triggered, within the eCRF, for adjudication by the CIAC. Details for the adjudication process are described in the adjudication charter.

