If any of the above listed outcome events fulfil the definition of SAEs as given in Section 10.3.2, the investigator must report them immediately (within 24 hours of the investigator's awareness) to the sponsor's pharmacovigilance department as described in Section 10.3.4. However, SUSARs that derive from these efficacy outcome events (as specify above ii – vii: vascular death, non-fatal stroke/MI, major amputation, acute limb ischemia, symptomatic VTE, thrombosis of arterio-venous graft or fistulas), including events indicative of those outcome events (details will be described in the adjudication charter and additional study specific guidance documents) will be waived from unblinding and are not subject to expedited reporting to health authorities. In case of unblinding, SUSARs may be submitted blinded, either expedited or aggregated, to investigators and IEC/IRB. Unblinded SUSAR reports are submitted only when required by local legislation.

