8.3.6 Cardiovascular and Death Events

Death will be reported with the known cause of death as a SAE. Additionally, an electronic adjudication package will be submitted to the CIAC. If the cause of death is unknown, then a cause of death will be assigned by the CIAC. In order not to delay reporting within the required timeframe, when the cause of death is not known, the event should be reported as "Death not otherwise specified." If follow-up reports are received with the actual cause of death, the report will be updated.

For cardiovascular events see Section 9.4.6.1

07 JUL 2021 Page: 52 of 90

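### Protocol 10.3.2 names death from disease progression as an event that cannot be an SAE, while 8.3.6 reports every death as an SAE and 8.1 reports every death as an AE or SAE

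*Protocol*

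**What the plan says.** Two parts of the protocol govern how a death is classified.

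The appendix works by exclusion. Among events that do not meet the AE definition, 10.3.1 lists "The disease/disorder being studied or expected progression, signs, or symptoms of the disease/disorder being studied, unless more severe than expected" for the participant's condition. Section 10.3.2 builds on this: an event outside that definition cannot be an SAE, "even if serious conditions are met (e.g., hospitalization for signs/symptoms of the disease under study, death due to progression of disease"). The bracket thus gives two examples, an admission and a death. The same section then lists a fatal outcome as the first SAE criterion.

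The body of the protocol works by inclusion. Section 8.3.6 reads: "Death will be reported with the known cause of death as a SAE". It adds a package for the CIAC and a holding term for deaths of unknown cause, so that reporting is not delayed. Section 8.1 requires "All deaths and events suspected to be related to cardiovascular disease, or other arterial or venous thrombosis events" to be reported as an AE or SAE and triggered in the eCRF for adjudication. Section 8.3.10 sends all deaths after randomization to the CIAC.

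Section 8.3.1 sets a 24-hour limit for reporting SAEs. SAP 6.4.2 plans summaries of TESAEs, tables or listings of treatment-emergent deaths and serious AEs, and an overview table with a row for AE-related deaths.

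**The concern.** An investigator who judges a death to be expected progression of ESRD has two instructions that cannot both be followed. Under 8.3.6 the death is an SAE. Under 10.3.2 it is the protocol's own example of an event that cannot be one. I found no statement that the body overrides the appendix or the reverse.

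The trial's primary objective is safety, and serious events and deaths are among its planned safety outputs. If classification depends on which section a site reads, such a death may miss 24-hour reporting and drop out of the SAE-based tables at some sites but not at others. Treatment is blinded as to active versus placebo, so there is no obvious reason for this to favour one arm. The likely harm is lost events and added noise, not a directional bias.

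**Working it through.** There is no figure to reproduce. The check takes one case, a death that the investigator attributes to expected progression of ESRD, through each section that applies.

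1. **10.3.1.** Expected progression of the studied disease is not an AE unless it is more severe than expected for that participant. If the investigator judges that it was not, the event is not an AE.
2. **10.3.2.** The rule is conditional: it bars SAE status only for events that are not AEs. The case meets the condition by step 1, and the section names a death of this kind as an example. Result: not an SAE.
3. **8.3.6.** Death is reported as an SAE whatever its cause. Result: an SAE. This contradicts step 2.
4. **8.1.** All deaths are reported as an AE or SAE. Result: at least an AE. This contradicts step 1.
5. **8.3.7.** This is the body section on disease-related events that do not qualify as AEs or SAEs. It names only expected access bleeding after dialysis, so it gives no support for excluding deaths.

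Next, the consequences of a site following steps 1 and 2:

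| Item | Depends on AE/SAE status? | Source |
|---|---|---|
| 24-hour reporting to the sponsor | Yes | Protocol 8.3.1 |
| TESAE tables, and the AE-based outputs on deaths, including the AE-related deaths row | Yes | SAP 6.4.2 |
| Submission of deaths to the CIAC | Required for all deaths, though 8.1 places the trigger next to the AE/SAE report | Protocol 8.1, 8.3.6, 8.3.10 |
| Record of death at withdrawal, with cause and vital status | Required for every death, though the cause is noted under AEs | Protocol 7.2 |
| Analysis of overall death and its components | Not stated to depend on it | SAP 6.2.1.1 |
| Primary endpoint (adjudicated major and clinically relevant non-major bleeding) | Not touched by this example | Protocol 9.4.2 |

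The exposure is therefore confined to the first two rows, with a small residual risk in the third and fourth if a site makes no AE entry at all.

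**The case against.** The strongest reply is that 10.3.2 is narrower than it looks. It reaches only events that are not AEs, and 10.3.1 restores anything more severe than expected. Because 5.2 excludes people with a life expectancy under 6 months, one can argue that any death in the main treatment period is more severe than expected. Several body sections also say plainly that deaths are reported and adjudicated, and investigators must assess each event's relation to ESRD (10.3.3), so the plan clearly expects ESRD-related events to be recorded. All of this limits the point. It does not remove it, because 10.3.2 itself offers a death as an example of what stays excluded.

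A reader might infer more than the documents support in four ways.

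- **That hospitalizations are caught in the same contradiction.** They are not. Section 8.3.6 concerns deaths only. Leaving out admissions for expected signs of the underlying disease agrees with 10.3.1 and is a matter of investigator judgement.
- **That 8.3.4 carries the exclusion into the reporting of all outcome events**, because 24-hour reporting there applies to those that "fulfil the definition of SAEs as given in Section 10.3.2". But 8.3.4 introduces the listed events as AEs that are also endpoints, so the reference is most naturally read as asking whether the event is serious.
- **That such deaths would not reach the CIAC or the DMC.** Three sections send all deaths to the CIAC, and what the DMC receives is set in a charter that is not among the documents.
- **That a number of missed deaths can be derived from the 40% five-year survival in 2.2.1.** That figure describes HD patients in general from onset. The trial excludes several high-risk groups, and no document gives the share of deaths that would be called progression.

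**Conclusion.** The protocol is wrong as written on one point: 10.3.2, read with 10.3.1, contradicts 8.3.6 and 8.1 on deaths due to progression of the disease. The consequence is possible variation between sites in 24-hour SAE reporting, in TESAE tables and in the AE-based death outputs. Total death counts, adjudication of deaths and the primary endpoint are largely protected.

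No numerical size can be given. The conclusion rests on two assumptions: that some deaths will be judged expected progression of ESRD, and that some sites will apply the appendix definition to them. The contradiction in the text depends on neither. It is worth correcting in a trial whose primary objective is safety, because it is a stated rule that conflicts with another and not merely a missing detail.

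**What to change.** Reconcile the sections in favour of what 8.3.6 and 8.1 already require for deaths:

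- Remove the death example from the bracket in 10.3.2.
- Add to 10.3.1 and 10.3.2 a sentence such as: the exclusion for expected disease progression does not apply to deaths; all deaths are reported as SAEs and submitted to the CIAC under Section 8.3.6.

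Removing the example alone is not enough, since the conditional rule in 10.3.2 and the exclusion in 10.3.1 would still lead to the same result.

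Limit the added sentence to deaths. Extending it to every outcome event listed in 8.3.4 would take in bleeding without qualification and would clash with the deliberate exception for expected access bleeding in 8.2.1 and 8.3.7. The hospitalization example can stay.

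The cost is a one-sentence clarification and possibly a few more SAE reports. No endpoint or analysis changes.
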